8. DRUG FORMULATION, AVAILABILITY, ADMINISTRATION AND TOXICITY INFORMATION

8.1. Orteronel

Investigational Product	Dosage Form and Strength	Manufacturer
Orteronel	100 mg tablets	Takeda Pharmaceutical Company, Ltd

Orteronel (chemical name, 6-[(7S)-7-hydroxy-6,7-dihydro-5H-pyrrolo[1,2-c]imidazol-7-yl]-N-methyl-2-naphthamide) is manufactured by Takeda Pharmaceutical Company, Ltd, Osaka, Japan.

Additional information can be found in the IB.

8.1.1. Labeling, Packaging, and Supply

Orteronel will be packaged in a round, white, high-density polyethylene (HDPE) bottles with a child-resistant cap and induction seal. Each bottle of active orteronel will be labeled with either a single-panel or multi-language booklet label containing pertinent study information, country-specific requirements, and a caution statement.

Orteronel will be supplied as pale red film-coated tablets. Each bottle will contain 64 tablets and each tablet will contain 100 mg of orteronel.

On Day 1 of each cycle, patients will be dispensed sufficient supplies until the next visit.

All study drugs must be kept in a secure place under appropriate storage conditions. Storage conditions for orteronel are included in the IB and on the product label.

8.1.2. Preparation and Administration of Investigational Products

Orteronel 300 mg PO BID continuous daily dosing

Patients will be instructed to take 300 mg orteronel (consisting of three 100-mg tablets at each administration) twice a day with or without food until discontinuation of study treatment/patient withdrawal. The doses of study drug should be taken at the same time each day, approximately 12 hours apart, but not less than 6 hours apart.

Missed doses of study drug may be taken later, provided that the time of dosing is at least 6 hours before the next scheduled dose. Otherwise, patients should resume dosing at the next scheduled time with the prescribed dose. Patients who experience Grade 1 or 2 nausea or vomiting may be advised to take the study drug with or following meals.

On Day 1 of each Cycle, patients will be asked about any missed doses. If a dose is missed, the missed dose will be recorded as “not taken.”

CONFIDENTIAL

STUDY DRUG: Orteronel

SCRI INNOVATIONS STUDY NUMBER: BRE 203

DATE OF PROTOCOL: Version 3.0 30 October 2013

8.1.3. Accountability of Investigational Products

The Principal Investigator (or designee) must maintain accountability for all study medication received and dispensed during his or her entire participation in the study. Proper drug accountability includes, but is not limited to:

- Continuously monitoring expiration dates if retest date is provided to the investigator
- Frequently verifying that actual inventory matches documented inventory
- Verifying that the drug accountability log is completed for the drug lot used to prepare each dose
- Verifying that all containers used are documented accurately on the log
- Verifying that required fields are completed accurately and legibly

If any dispensing errors or discrepancies are discovered, SCRI Innovations must be notified immediately.

The investigator must maintain a current inventory (drug accountability log) of all study medication delivered to the site, inventory at the site, and patients' use records. This log must accurately reflect the drug accountability of the study medication at all times. The log should include all required information as a separate entry for each patient to whom study medication is dispensed.

The sites should destroy any unused product at the end of the study (or expired product, if any, during the study), per the site's SOPs for doing so. A certificate of destruction that includes a description of the supplies, quantity destroyed, and method of destruction should be returned to the Sponsor.

9. RESPONSE EVALUATIONS AND MEASUREMENTS

9.1. Definitions

Response and progression will be evaluated in this study using the RECIST Version 1.1 (Eisenhauer et al. 2009). Lesions are either measurable or non-measurable using the criteria provided below. The term "evaluable" in reference to measurability will not be used, as it does not provide additional meaning or accuracy.

CONFIDENTIAL

STUDY DRUG: Orteronel

SCRI INNOVATIONS STUDY NUMBER: BRE 203

DATE OF PROTOCOL: Version 3.0 30 October 2013

9.2. Baseline Eligibility

Measurable Disease:	
Tumor lesions: Must be accurately measured in at least one dimension (longest diameter in the plane of measurement is to be recorded) with a minimum size of:
 
• 10 mm by CT scan (CT scan slice thickness no greater than 5 mm).• 10 mm caliper measurement by clinical exam (lesions that cannot be accurately measured with calipers should be recorded as non-measurable).• 20 mm by chest x-ray. 
Skin lesions: Documentation by color photography, including a ruler to estimate the size of the lesion, is recommended.
 
Malignant lymph nodes: To be considered pathologically enlarged and measurable, a lymph node must be >15 mm in short axis when assessed by CT scan. At baseline and in follow-up, only the short axis will be measured and followed.

Non-Measurable Disease:	All other lesions, including small lesions (longest diameter <10 mm or pathological lymph nodes with >10 - to <15 -mm short axis) as well as truly non-measurable lesions. Lesions considered truly non-measurable include: leptomeningeal disease, ascites, pleural or pericardial effusion, inflammatory breast disease, lymphangitic involvement of skin or lung, abdominal masses, abdominal organomegaly identified by physical exam that is not measurable by reproducible imaging requirements.
Target Lesions:	
The most reproducible measurable lesions, up to a maximum of 2 lesions per organ and 5 lesions in total, representative of all involved organs should be identified as target lesions and recorded and measured at baseline.
 
Target lesions should be selected on the basis of their size (lesions with the longest diameter), should be representative of all involved organs, and in addition should be those that lend themselves to reproducible repeated measurements. Pathological nodes which are defined as measurable and that may be identified as target lesions must meet the criterion of a short axis of >15 mm by CT scan.
 
A sum of the diameters (longest for non-nodal lesions, short axis for nodal lesions) for all target lesions will be calculated and reported as the baseline sum diameters. If lymph nodes are to be included in the sum, then as noted above, only the short axis is added into the sum. The baseline sum diameters will be used as reference to further characterize any objective tumor response.

Non-Target Lesions:	
All other lesions should be identified as non-target lesions at baseline. Measurements of these lesions are not required, but the presence or absence of each should be noted throughout follow-up.

9.2.1. Guidelines for Evaluation of Measurable Disease

All measurements should be taken and recorded in metric notation, using a ruler or calipers. All baseline evaluations should be performed as closely as possible to the beginning of treatment, as per protocol screening requirements.

CONFIDENTIAL

STUDY DRUG: Orteronel

SCRI INNOVATIONS STUDY NUMBER: BRE 203

DATE OF PROTOCOL: Version 3.0 30 October 2013

The same method of assessment and the same technique should be used to characterize each identified and reported lesion at baseline and during follow-up. Imaging-based evaluation is preferred to evaluation by clinical examination when both methods have been used to assess the anti-tumor effect of a treatment.

Clinical Lesions:	Clinical lesions will only be considered measurable when they are superficial (e.g., skin nodules and palpable lymph nodes). In the case of skin lesions, documentation by color photography, including a ruler to estimate the size of the lesion, is recommended.
Chest X-ray:	Lesions on chest X-ray are acceptable as measurable lesions when they are clearly defined and surrounded by aerated lung. However, CT is preferable.
Conventional CT and MRI:	CT and MRI are the best currently available and reproducible methods to measure target lesions selected for response assessment. Conventional CT and MRI should be performed with cuts of 10 mm or less in slice thickness, contiguously. Spiral CT scan should be performed using a 5-mm contiguous reconstruction algorithm. This applies to tumors of the chest, abdomen, and pelvis. Head and neck tumors and those of extremities usually require specific protocols.
Ultrasound:	When the primary trial endpoint is objective response, ultrasound should not be used to measure tumor lesions. It is, however, a possible alternative to clinical measurements of superficial palpable lymph nodes, subcutaneous lesions, and thyroid nodules. Ultrasound may also be useful to confirm the complete disappearance of superficial lesions usually assessed by clinical examination.
Endoscopy and Laparoscopy:	Use of endoscopy and laparoscopy for objective tumor evaluation has not yet been fully and widely validated. Therefore, use of these techniques for objective tumor response should be restricted to validation purposes in specialized centers. Such techniques can be useful in confirming complete pathological response when biopsies are obtained.
Tumor Markers:	Tumor markers alone cannot be used to assess response. If markers are initially above the upper limit of normal, they must normalize for a patient to be considered in complete clinical response when all lesions have disappeared.
Cytology and Histology:	Cytology and histology can be used to differentiate between PR and CR in rare cases (e.g., after treatment to differentiate between residual benign lesions and residual malignant lesions in tumor types such as germ cell tumors).

CONFIDENTIAL

STUDY DRUG: Orteronel

SCRI INNOVATIONS STUDY NUMBER: BRE 203

DATE OF PROTOCOL: Version 3.0 30 October 2013

9.2.2. Response Criteria

Evaluation of Target Lesions

Complete Response (CR): Disappearance of all target lesions.

Partial Response (PR): At least a 30% decrease in the sum of the longest diameter (LD) of target lesions, taking as reference the baseline sum LD.

Stable Disease (SD): Neither sufficient shrinkage to qualify for PR nor sufficient increase to qualify for PD, taking as reference the smallest (nadir) sum LD since the treatment started.

Progressive Disease (PD): At least a 20% increase in the sum of the LD of target lesions, taking as reference the smallest (nadir) sum since the treatment started, or the appearance of one or more new lesions. Requires not only 20% increase, but absolute increase of a minimum of 5 mm over sum.

Evaluation of Non-Target Lesions

Complete Response (CR): Disappearance of all non-target lesions and normalization of tumor markers. All lymph nodes must be non-pathological in size (<10 mm short axis).

Stable Disease (SD): Persistence of one or more non-target lesions and/or persistence of tumor marker level above the normal limits.

Progressive Disease (PD): Appearance of one or more new lesions and/or unequivocal progression of existing non-target lesions. When the patient also has measurable disease, to achieve “unequivocal progression” on the basis of the non-target disease, there must be an overall level of substantial worsening in non-target disease such that, even in presence of SD or PR in the target disease, the overall tumor burden has increased sufficiently to merit discontinuation of therapy.

Evaluation of Best Overall Response

The best overall response is the best response recorded from the start of the treatment until disease progression/recurrence (taking as reference for progressive disease the smallest measurements recorded since the treatment started). In general, the patient's best response assignment will depend on the achievement of both measurement and confirmation criteria.

Confirmation of response (by repeat scans after 4 weeks or as specified in the protocol) is required for trials in which response rate is the primary endpoint, but is not required in randomized trials or trials with primary survival endpoints (i.e., where response is not a primary endpoint).

CONFIDENTIAL

STUDY DRUG: Orteronel

SCRI INNOVATIONS STUDY NUMBER: BRE 203

DATE OF PROTOCOL: Version 3.0 30 October 2013

Target Lesions	Non-Target Lesions	New Lesions	Overall Response
CR	CR	NO	CR
CR	SD	NO	PR
CR	NE	NO	PR
PR	SD OR NE	NO	PR
SD	SD OR NE	NO	SD
PD	ANY	YES OR NO	PD
ANY	PD	YES OR NO	PD
ANY	ANY	YES	PD

In some circumstances, it may be difficult to distinguish residual disease from normal tissue. When the evaluation of a CR depends upon this determination, it is recommended that the residual lesion be investigated by fine needle aspirate or biopsy to confirm the CR status.

When nodal disease is included in the sum of target lesions, and the nodes decrease to “normal” size (<10 mm), they may still have a measurement reported on scans. This measurement should be recorded even though the nodes are normal in order not to overstate progression, should it be based on increase in size of the nodes. As noted earlier, this means that patients with CR may not have a total sum of “zero” on the eCRF.

Non-Measurable Disease Only

When a patient only has non-measurable disease: this circumstance arises in some trials when it is not a criterion of study entry to have measurable disease. The same general concepts apply here as noted above, however, in this instance; there is no measurable disease assessment to factor into the interpretation of an increase in non-measurable disease burden. Because worsening in non-target disease cannot be easily quantified (by definition: if all lesions are truly non-measurable) a useful test that can be applied when assessing patients for unequivocal progression is to consider if the increase in overall disease burden based on the change in non-measurable disease is comparable in magnitude to the increase that would be required to declare PD for measurable disease: i.e. an increase in tumor burden representing an additional 73% increase in ‘volume’ (which is equivalent to a 20% increase diameter in measurable lesion). Examples include an increase in a pleural effusion from ‘trace’ to ‘large’, an increase in lymphangitic disease from localized to widespread, or may be described in protocols as ‘sufficient to require a change in therapy’. If ‘unequivocal progression’ is seen, the patient should be considered to have had overall PD at that point. While it would be ideal to have objective criteria to apply non-measurable disease, the very nature of that disease makes it impossible to do so; therefore the increase must be substantial.

CONFIDENTIAL

STUDY DRUG: Orteronel

SCRI INNOVATIONS STUDY NUMBER: BRE 203

DATE OF PROTOCOL: Version 3.0 30 October 2013

10. STATISTICAL CONSIDERATIONS

10.1. Statistical Design

This is an open-label multicenter study to be conducted in 2 clinical stages. All patients will receive orteronel PO at a dose of 300 mg twice daily (BID).

Lead-in Phase: The first 6 patients treated will be evaluated to confirm the safety and feasibility of this regimen. All 6 patients will be followed weekly for toxicities during the first 4 weeks of treatment. After all 6 patients complete at least 4 weeks of treatment, and if no prohibitive toxicities are identified, continuous study treatment will begin.

Continuous Study Treatment: Patients will continue to be enrolled into their respective cohorts, based on their tumor specificities, to either Cohort 1 (ER-/PR-/HER2-/AR+) or Cohort 2 (ER+ and/or PR+/AR+).

10.2. Analysis Population

The intent-to-treat (ITT) population will consist of all patients enrolled in the trial. Screen failures will not be included in the ITT population.

The Safety population will consist of all patients receiving at least one dose of study drug.

10.3. Sample Size Considerations

Up to 86 patients will be enrolled into this study.

Sample size computations are as follows for each patient cohort.

Cohort 1: For patients with ER-/PR-/HER2-/AR+ tumors, the expected response rate with standard anti-estrogen therapy is expected to be zero. Therefore, a response rate of at least 10% with orteronel therapy would indicate activity and would lead to further investigation. Assuming an evaluable population of 28 patients, the exact 95% confidence interval (CI) for a hypothesized response rate of 11% is (2.4%, 28.6%). In order to incorporate an early stopping rule, Simon's two-stage design is applied using $\alpha = 0.10$ and $\text{power} = 0.80$ with comparison of the hypothesized response rate of 11% versus a conservative estimate of 2%. Initially, 19 patients will be enrolled in this cohort, and if no responses are observed, recruitment to this cohort will stop. Otherwise, enrollment in Cohort 1 will continue to full accrual of 28 evaluable patients. To account for an unevaluable rate of 10%, a total of 31 patients will be enrolled in this cohort.

Cohort 2: For patients with ER+ and/or PR+/AR+ tumors, published data on exemestane as third-line hormonal therapy in postmenopausal women indicate a response rate of 13% and a clinical benefit rate (CR, PR, or SD >24 weeks) of 30%. It is hypothesized that treatment with orteronel in this patient population will produce similar results. Assuming an evaluable population of 50 patients, the exact 95% CI for a hypothesized response rate of 14% is (5.8%, 26.7%). In order to incorporate an early stopping rule, Simon's two-stage design is applied using $\alpha = 0.10$ and $\text{power} = 0.80$ with comparison of the hypothesized response rate of 14% versus a conservative estimate of 5.1%. Initially, 26 patients will be enrolled in this cohort, and if one or no responses are observed, recruitment into this cohort will stop. Otherwise, enrollment in

CONFIDENTIAL

STUDY DRUG: Orteronel

SCRI INNOVATIONS STUDY NUMBER: BRE 203

DATE OF PROTOCOL: Version 3.0 30 October 2013

Cohort 2 will continue to full accrual of 50 evaluable patients. To account for an unevaluable rate of 10%, a total of 55 patients will be enrolled in this cohort.

10.4. Planned Interim Analyses

Based on Simon's two-stage design, each cohort individually will undergo an interim analysis for efficacy.

Cohort 1: After enrollment of the first 19 evaluable patients and if no responses are observed, recruitment to this cohort will stop due to lack of efficacy. Otherwise, enrollment will continue to full accrual of 28 evaluable patients. If two or more patients exhibit response at the final analysis, the trial will be considered successful with respect to this patient population.

Cohort 2: After enrollment of the first 26 evaluable patients and if one or no responses are observed, recruitment to this cohort will stop due to lack of efficacy. Otherwise, enrollment will continue to full accrual of 50 evaluable patients. If five or more patients exhibit response at the final analysis, the trial will be considered successful with respect to this patient population.

10.5. Statistical Analyses

All statistical analyses will be performed using SAS 9.1.3 or the current version of SAS available at the time of analysis.

In general, data will be listed and/or summarized and tabulated. Descriptive statistics, such as means, median, standard deviation, minimum and maximum for continuous variables, and counts and percentages for discrete variables, will be used to summarize data as appropriate.

10.6. Efficacy Measures

The primary efficacy endpoints for both Cohort 1 and Cohort 2 are the RR and DCR.

Secondary efficacy endpoints are PFS and OS.

Efficacy analyses will include all patients in the ITT population.

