10.6.1. Primary Endpoints

The RR is defined as the percentage of responders (CR+PR) among those patients who are evaluable for response. Response rate will be presented as the point estimate along with 95% confidence intervals calculated using both asymptotic normal approximation and exact binomial methods.

The DCR is defined as the percentage of patients who do not exhibit progression (CR+PR+SD) among those patients who are evaluable for response at 6 months. Disease control rate will be presented as the point estimate along with 95% confidence intervals calculated using both asymptotic normal approximation and exact binomial methods.

CONFIDENTIAL

STUDY DRUG: Orteronel

SCRI INNOVATIONS STUDY NUMBER: BRE 203

DATE OF PROTOCOL: Version 3.0 30 October 2013

Page 55 of 80

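### RR and DCR are divided by an undefined evaluable set that contradicts the ITT statement in 10.6; the 6-month DCR is the result most exposed

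*Combined protocol and SAP*

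**What the plan says.** Section 10.2 defines two sets. For the first it says "The intent-to-treat (ITT) population will consist of all patients enrolled in the trial"; the second is the Safety population. Section 10.6 names RR and DCR as primary in both cohorts and adds "Efficacy analyses will include all patients in the ITT population".

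Section 10.6.1 uses other denominators. For RR: "The RR is defined as the percentage of responders (CR+PR) among those patients who are evaluable for response". For DCR, non-progression is counted "among those patients who are evaluable for response at 6 months".

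The sample size is also built on evaluable patients. For Cohort 1, 10.3 begins "Assuming an evaluable population of 28 patients" and ends "To account for an unevaluable rate of 10%, a total of 31 patients will be enrolled in this cohort". Cohort 2 has the same structure with 50 and 55. The first look is described in two ways. Section 10.3 and the synopsis count enrolled patients: "Initially, 19 patients will be enrolled in this cohort, and if no responses are observed, recruitment to this cohort will stop". Section 10.4 counts evaluable ones: "After enrollment of the first 19 evaluable patients and if no responses are observed, recruitment to this cohort will stop". Under 10.4, success is two or more responses in Cohort 1 and five or more in Cohort 2.

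No section says what makes a patient evaluable for response. Section 9.1 drops the word as a description of measurability, although inclusion criterion 2 uses it.

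**The concern.** The two statements cannot both govern the primary endpoints: a rate is computed either on everyone enrolled or on a subset. If a subset is meant, three foreseeable groups have no stated status.

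- Patients with no post-baseline scan because of early death, clinical progression or toxicity.
- Bone-only patients. Section 3.1 admits them, but 9.2.2 defines PR only by target-lesion diameters, and 7.4.2 makes bone scans conditional on clinical need.
- For DCR, patients who stop treatment without documented progression before month 6.

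In an open-label single-arm trial, who counts should be settled before responses are known. Otherwise membership of the denominator can follow outcome. DCR has the most at stake: it has no decision rule, so the estimate and its interval are the result.

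**Working it through.** **1. The plan's own design.** Inputs from 10.3 and 10.4:

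- Cohort 1: null 2%, target 11%, looks at 19 and 28, stop at 0, success at 2 or more.
- Cohort 2: null 5.1%, target 14%, looks at 26 and 50, stop at 1 or fewer, success at 5 or more.

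With first look n1, stopping bound r1, final n and success count s, P(success) is the sum over x > r1 of Bin(x; n1, p) × P(X2 ≥ s − x), where X2 ~ Bin(n − n1, p).

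For Cohort 1 this is P(x ≥ 2) + P(x = 1) × P(X2 ≥ 1):

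- At 2%: 0.98^19 = 0.6812; 19 × 0.02 × 0.98^18 = 0.2642; remainder 0.0546; 1 − 0.98^9 = 0.1663. Alpha = 0.0546 + 0.2642 × 0.1663 = 0.0985.
- At 11%: 0.89^19 = 0.1092; 19 × 0.11 × 0.89^18 = 0.2566; remainder 0.6342; 1 − 0.89^9 = 0.6496. Power = 0.6342 + 0.2566 × 0.6496 = 0.801.

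The same sum for Cohort 2 gives alpha 0.0973 and power 0.806. The stated 0.10 and 0.80 reproduce on the evaluable basis.

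**2. The same cut-offs on other sets.** If unevaluable patients count as non-responders, p is multiplied by the evaluable fraction.

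| Patients counted | Cohort 1 alpha / power | Cohort 2 alpha / power |
|---|---|---|
| 28/50 evaluable (10.4) | 0.0985 / 0.801 | 0.0973 / 0.806 |
| All 31/55, all able to respond at the planning rates | 0.111 / 0.827 | 0.124 / 0.842 |
| All 31/55, 10% counted as non-responders | 0.094 / 0.780 | 0.089 / 0.773 |

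The second row is the ceiling for alpha if every surplus patient is counted. Averaged over a random evaluable number at the plan's 10% loss, alpha is 0.098/0.095.

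**3. RR as reported.** 3/28 = 10.7% against 3/31 = 9.7%; 7/50 = 14.0% against 7/55 = 12.7%. The denominator moves RR by about one point and leaves the response count unchanged.

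**4. Who can lack a 6-month assessment.** Cycles last 28 days and CT falls on Day 1 of Cycles 3, 5 and 7 (7.4, 7.4.2), that is weeks 8, 16 and 24 (6 × 28 = 168 days for the last). Section 7.5 and Appendix E require an end-of-treatment CT only if progression is undocumented and the last assessment was more than 8 weeks earlier. After that, 7.6.1 leaves imaging to clinical need. A patient who stops for toxicity at week 18, with an end-of-treatment visit that week, was scanned two weeks before. No CT is then due at that visit, and none is scheduled at week 24.

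**5. Effect on DCR.** Take 15 controlled patients in Cohort 2, which is 30% of 50, borrowing the published clinical benefit rate in 10.3 for scale only:

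- ITT: 15/55 = 27.3%
- 50 evaluable, missing counted as not controlled: 15/50 = 30.0%
- five without a 6-month assessment dropped (assumption): 15/45 = 33.3%

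**The case against.** The strongest reply is that 10.4 already ties the decision to counted sets, the first 19 and 28 or 26 and 50 evaluable patients, and that on those sets the design meets its error rates. That stands. A reader might infer that the Simon cut-offs are wrong or that alpha is uncontrolled; the documents do not support this. Section 5 enrols up to 31 and 55, which can be read as a ceiling. If accrual ends at 28/50 evaluable within that ceiling, alpha is 0.095/0.092 and power 0.792/0.794 at 10% loss. Values above 0.10 need surplus patients to be counted and less loss than planned.

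Three other stronger readings also fail.

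- Taking stage 1 in 10.3 literally as enrolled patients would give power 0.781/0.778 at 10% loss. But 10.3 starts from an evaluable population and 10.4 is explicit, so this is loose wording.
- Patients who progress before month 6 might seem to drop out of DCR. Section 10.6.1 defines control as absence of progression, so they naturally count as not controlled. The gap is limited to those who stop without documented progression.
- The design might seem undersized because bone-only patients are admitted. The documents give neither their expected share nor whether the planning rates refer to measurable disease.

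It is also fair that nothing in the documents says how many patients will lack a 6-month assessment. Five of 50 equals the plan's 10% unevaluable share but remains an assumption. What the reply does not answer is the conflict between 10.6 and 10.6.1, or the absence of any definition.

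**Conclusion.** The point holds and should be fixed. Sections 10.6 and 10.6.1 give incompatible denominators for both primary endpoints, and the set in 10.6.1 is undefined. The Simon arithmetic is right. The go/no-go decision is exposed through who is called evaluable. As a minor matter, it is also exposed if the cut-offs are applied to all 31/55 (alpha up to 0.111/0.124, or power 0.780/0.773 with 10% counted as non-responders). For RR the effect on the reported rate is about one point.

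The main consequence is for DCR. Leaving out patients who stop without progression before week 24 raises it relative to counting them as not controlled: from 30.0% to 33.3% in the illustration, against 27.3% on ITT. The direction follows from the definition. The size rests on the assumed 15 controlled and five dropped patients.

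**What to change.** 1. In 10.2, define one response-evaluable set that does not depend on outcome, for example treated patients with a baseline tumour assessment. Keep patients with no post-baseline scan because of death, clinical progression or toxicity in it as non-responders. State whether bone-only and other non-measurable patients count for RR.
2. In 10.6 and 10.6.1, name that set as the primary denominator for RR and DCR. Report ITT RR and DCR alongside, and keep PFS and OS on ITT.
3. Tie DCR to the scheduled Cycle 7 Day 1 (week 24) scan. Count patients who progressed, died or have no assessment by then as not controlled.
4. Align 10.3 and the synopsis with 10.4 (19 and 26 evaluable). Apply the cut-offs to the first 19/28 and 26/50 evaluable patients in order of enrolment, with any surplus descriptive. If fewer are evaluable within 31/55, report the attained alpha and power; enrolling more could breach the 86-patient limit.

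The cost is wording and slightly lower reported RR and DCR. If the planning rates refer to scanned patients only, keeping unscanned patients in at 28/50 lowers power to about 0.776/0.768 at 5% unscanned and 0.749/0.726 at 10% (target rates × 0.95 and × 0.90). If the rates also refer to measurable disease and bone-only patients stay in as non-responders, 10% of each gives 0.694/0.636 (rates × 0.9 × 0.9 = × 0.81). These shares are assumptions. The sponsor should say which patients the planning rates describe and restate power accordingly.
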